### Baseline, Intermediate and Final MRI:

Each subject will undergo similar scan protocol at baseline, intermediate and final MRI. Anatomical landmarks will be used to match images (baseline, intermediate and final) in the same patient from the three time points spread over an intervals of 18 months. These landmarks include arterial bifurcations, vertebrae, proximity of other vessels and patterns of fat and muscle. Since the slice volume would be planned centered at the area of interest for all the studies (initial and repeat); the exact Z-location of each slice would be known and reproducible for acquisition and comparative measurements.

### Specific Aims:

A # 1: Characterization of plaque constituent's i.e. fibrous cap (FC), fat and hemorrhage within the carotid artery plaque by multiple MRI sequences: 3-point Dixon (3PD) and MCW sequences (3-D TOF, T1W, T2W & PDW)].

Rationale: Using MRI we will determine the plaque characteristics, which may help understand the increase risk of stroke in this patient population.

Data analysis: The plaque size and morphology (vessel wall area) will be determined as described in section below.

Expected results: We anticipate that the plaque morphology will be accurately and more importantly reliably determined and followed up by a combination of MCW and 3PD sequences.

Measurement of Changes in Carotid Plaque Size, Characteristics and Morphology Using Multiple-Contrast-Weighted High-Resolution MR Imaging:

To minimize errors and to improve contrast to noise ratio, five contiguous images centered at the point of interest will be analyzed and the results will be averaged. The vessel wall area will be calculated by measuring the area of the lumen and the total artery area (vessel wall area = total artery area – lumen area). The vessel wall area and total artery area will be determined by tracing contours along the boundaries. The areas will be calculated using a semi-automated analysis tool (MASS Analytical Software, Medis Medical Imaging Systems, Leiden, The Netherlands). In the selected images, the maximum, minimum and average wall thickness will also be measured.

Identification of plaque constituents will be facilitated by multiple contrast-weighted MR images and also 3-point Dixon (selective water/fat) (17, 40). Table 1 & 2 shows the MR signal intensities that are associated with the various plaque components depending on the type of weighting that is used. The different signal intensities that result from the use of MCW (table 1) and 3-point Dixon technique (table 2) images improve the accuracy of identifying the plaque constituents.

Table 1. Criteria for identifying intraplaque hemorrhage and lipids using 3-point Dixon technique.

Plaque Feature	Water	Fat
Calcification	Hypo-intense	Hypo-Intense
Hemorrhage	Hyper-Intense	Hypo-intense
Lipid	Hypo-Intense	Hyper-intense

Table 2. Criteria for identifying intraplaque hemorrhage and lipids using MCW imaging.

Plaque Feature	TOF	T1W-BB-FSE	T2W-BB-FSE
-----------------------	------------	-------------------	-------------------

Calcification	Hypo-Intense	Hypo-Intense	Hypo-Intense
Hemorrhage	Hyper-Intense	Hyper-Intense to Iso-Intense	Hypo-Intense to Iso-Intense
Lipid	Hypo-Intense	Hyper-Intense to Iso-Intense	Hypo-Intense to Iso-Intense

If complex plaques are present in any of the study subjects, the area of lipid core regions, the thickness of fibrous caps and the size of calcifications will be measured.

A # 3: To assess the longitudinal change in the carotid artery plaque characteristics (inflammation and morphology) as therapy progresses during the study period. Also to see if there is a predictable relationship between inflammation (pattern of enhancement) and vulnerable features within a plaque

Rationale: High-resolution MRI methods have shown that changes in the size and morphology of arterial plaques occur over time following the initiation of therapy (17, 40, 41). DCE-MRI parameters in plaques have been shown to correlate with histopathological measurement of inflammatory cell content and neovasculature (42, 43). For e.g. carotid artery wall thickness has been measured by MRI and has been associated with serum markers of inflammation (44). High resolution anatomical MRI has demonstrated that changes in the size of carotid artery plaques occur over time in patients who were receiving therapy (41). It is our hypothesis that the characteristics of arterial plaques in this patient population will change favorably over the duration of this study (36 months) and these changes will be measurable by DCE and high spatial resolution MRI.

Data analysis: The DCE-MRI dynamic enhancement parameters (Ktrans and  $\square_p$ ) will be determined as described in section below. The plaque size and morphology (vessel wall area) will be determined as described in SA # 1.

Statistical analysis: The three parameters mentioned above (Ktrans,  $\square_p$ , vessel wall) continuous variables. Before performing the statistical modeling we will check first to see if the distributions of these variables are normal; otherwise, we will use log transformation prior to the modeling of these parameters. We will first compute the mean, median, and standard deviation at each time point for these parameters. We will plot these data by patient over the 3 time points to examine the longitudinal profiles. We will use the linear mixed effects model (random coefficient model with random intercept and slope) with these parameters serving as dependent variables. The independent variables will be the time indicator and other potential confounders that we may need to control (e.g. age, gender, race, and body mass index). The interest in this model is the coefficient associated with the time indicator, which allows us to obtain the adjusted population mean estimate of these parameters at each of these time points. Since we have the best linear unbiased prediction estimates of the random intercepts and slopes for each subject,

we will be able to examine individual subject profiles and assess the temporal trend for each subject. Thus this random coefficient linear mixed effects model will allow us to obtain the overall adjusted mean estimate ( $K_{trans}$ ),

for each of the individual subjects, overall across all above mentioned time points, and at each of the time points.

To assess the association between the vessel wall area, and  $K_{trans}$  and

linear mixed effects models (random coefficient models) to obtain the estimates of fixed effects.

We will carry out 2 analyses in these models, we will use vessel wall area as the dependent variable and  $K_{trans}$  and

potential confounders if necessary. The slope estimate from these models is interpreted as a measure of adjusted association between the changes in plaque size and morphology, and DCE-MRI dynamic enhancement parameters.

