### **Introduction:**

Radiation therapy (XRT) is critical for the treatment of many benign and malignant neoplasms. It is well established that cancer survivors who have undergone XRT exhibit a long-term survival rate that significantly lags behind age and gender-matched population controls (7-11). Several scientific studies and publications have demonstrated that, of all etiologies of non-cancer mortality, cardiovascular disease (CVD) remains the most significant cause of morbidity and mortality in cancer survivors (7-11). Until recently radiation vasculopathy has attracted little research attention, because patients would often succumb to their malignancy before the vascular conditions manifested clinically (8). This is no longer the rule as more patients are now "outliving" their malignancies and are presenting with the long-term sequelae of cancer treatments (9). Sequelae and manifestations of accelerated atherosclerosis have been identified in the vasculature of almost every organ system (12-15). Atherosclerotic plaques that are susceptible to rupture, termed "vulnerable" or "unstable" consist of a large necrotic core made substantially of lipids and cell debris and a thin, collagen-poor fibrous cap (3, 16-18). Another characteristic of unstable plaques is that they contain numerous inflammatory cells. It has been documented that inflamed plaque and those with a large lipid core and thin fibrous cap are more likely to progress and cause clinical events than those without these features (19-21). Inflammation plays a major role in the onset, progression and destabilization of arterial plaque (22-27). Fig 1. Shows a brief overview of pathobiology and progression of arterial atherosclerosis.

Fig 1: Overview of pathobiology and progression of arterial atherosclerosis

Therefore imaging the vasculature for both its inflammatory state and presence of type of disease is very important (28-30). The potential of magnetic resonance imaging (MRI) to characterize arterial plaques has been extensively studied (1, 31-33). MRI due to its ability of tissue characterization, superior resolution, lack of radiation, non invasiveness is an ideal modality for *in vivo* study of arterial plaques.

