## Aims

The purpose of this study is to assess carotid artery MRI plaque characteristics in 100 asymptomatic cancer survivors with history of chest, head and neck radiotherapy (HNXRT) and with subclinical atherosclerosis. Another objective is to analyze plaque changes in the same group after initiation of medical treatment for 18 and 36 months.

The following specific aims (A), research questions (RQ) and hypotheses (H) will be addressed.

A 1: To characterize the plaque constituents including fibrous cap (FC), lipid core and hemorrhage within the carotid plaque by MRI

RQ 1a: What are the predominant plaque constituents?

RQ 1b: Is there a predominance of complex and vulnerable plaque features in the neck arterial vasculature of cancer survivors?

H 1: We hypothesize that there is a predominance of vulnerable plaque in carotid arterial vasculature of HNXRT patients due to the phenomenon of radiation vasculopathy.

A 2: Determine the correlation between plaque inflammation (direct measure by MRI) with serum markers of inflammation through blood tests (hsCRP, LpPLA2, IL-6) and metabolomics

and other tests of cardiac or vascular dysfunction (echocardiography and computerized tomography coronary calcium score studies).

RQ 2: Is there any correlation between the direct and surrogate markers of inflammation?

H 2: We hypothesize that there is a predictable correlation between the direct and surrogate measures of inflammation.

A 3: To assess the longitudinal change in the artery plaque characteristics (inflammation and morphology) with treatment.

RQ 3: Is there a predictable relationship between inflammation (pattern of enhancement-contrast kinetics) and vulnerable features within a plaque?

H 3: We hypothesize that changes in plaque characteristics pre and post treatment would correlate with contrast agent dynamics over time.

A 4: To determine the efficacy of comprehensive treatment (life style modification + statin) versus (life style modification + placebo).

RQ 4: Is one regimen better than the other in cancer survivors with subclinical atherosclerosis?

H 4: We hypothesize that comprehensive treatment (life style modification + statin) would have better inflammation control and favorable plaque modification than life style modification alone as measured by parameters in (A2 & A3).

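### RQ 3 asks whether contrast kinetics relate to vulnerable plaque features, but the readable A # 3 models contain only vessel wall area, a measure of size, and the plan has no rule for recording an absent feature

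*Combined protocol and SAP*

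**What the plan says.** **The question.** Under Aims, RQ 3 reads "Is there a predictable relationship between inflammation (pattern of enhancement-contrast kinetics) and vulnerable features within a plaque". A # 3 in the Specific Aims section repeats it: "Also to see if there is a predictable relationship between inflammation (pattern of enhancement) and vulnerable features within a plaque". H 3 is wider: it expects that "changes in plaque characteristics pre and post treatment would correlate with contrast agent dynamics over time".

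**What counts as vulnerable.** The Introduction says that vulnerable plaques "consist of a large necrotic core made substantially of lipids and cell debris and a thin, collagen-poor fibrous cap". A 1 sets out "To characterize the plaque constituents including fibrous cap (FC), lipid core and hemorrhage within the carotid plaque by MRI". The Précis says that the MRI techniques will be used to identify and measure hemorrhage, necrotic core and fibrous cap.

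**What is analysed.** The A # 3 data analysis paragraph states "The plaque size and morphology (vessel wall area) will be determined as described in SA # 1". The A # 3 statistical analysis names three continuous parameters: Ktrans, a second kinetic parameter whose symbol is not legible, and vessel wall. For the association between morphology and kinetics it states "we will use vessel wall area as the dependent variable".

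**What is measured, and when.** The text on A # 1 begins "If complex plaques are present in any of the study subjects, the area of lipid core regions, the thickness of fibrous caps" and goes on to the size of calcifications. Complex plaque is not defined, hemorrhage is not in this list, and nothing says what to record when a feature is absent. The section on baseline, intermediate and final MRI gives every subject a similar scan protocol at all three visits.

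**The concern.** The variable in the model is not the variable in the question. Wall area can stay the same while composition changes, and can change while composition stays the same. A null wall-area slope could therefore be read as showing no link between inflammation and vulnerability when a link exists. A positive slope could be read as a link with vulnerability when it is only a link with plaque size.

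If the gap is noticed late, the features, cut-offs and subset of subjects will be chosen after the data have been seen. The measurement condition adds to this. The Examination Plan Overview starts treatment on elevated blood markers or plaque on MRI, so subjects without plaque can be in the study, and the plan does not say what feature value they carry.

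**Working it through.** **1. Question against model.**

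| Item | In RQ 3 or its definitions | In a readable A # 3 model |
|---|---|---|
| Lipid or necrotic core | Yes (Introduction, A 1) | No |
| Fibrous cap | Yes (Introduction, A 1) | No |
| Hemorrhage | Yes (A 1) | No |
| Vessel wall area | No | Yes, as outcome |
| Ktrans and second kinetic parameter | Yes (contrast kinetics) | Yes |

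The kinetic side of RQ 3 is modelled. On the feature side, none of the three features is.

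**2. Why wall area cannot stand in.** By the plan's definition, W = total artery area − lumen area. Split the wall into lipid core L, hemorrhage H and remaining tissue F, so that W = L + H + F. If an amount x of lipid core is replaced by fibrous tissue, L falls by x, F rises by x, and the change in W is −x + x = 0. The plaque has become less vulnerable by the Introduction's description, and the outcome has not moved.

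**3. Could lost text explain the gap?** Words are missing after Ktrans in the association sentences. The intact text still settles it. The plan counts three parameters and all three are accounted for. The A # 1 and A # 3 data analysis paragraphs both equate size and morphology with vessel wall area, and the A # 3 expected results equate plaque size with it.

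**4. The plan's own figure.** For aim 3 the Sample Size section gives 92 subjects, effect size 0.28, three measurements, alpha 0.05 and power above 99%. Using one-way ANOVA with 92 per time point, the noncentrality is k·n·f² = 3 × 92 × 0.28² = 21.64, with 2 and 3 × (92 − 1) = 273 degrees of freedom. Power is 0.990, so the figure reproduces. It powers a change over time in one continuous parameter. It says nothing about the association with features in RQ 3.

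**5. What conditional measurement could cost.** The share of subjects with complex plaque and the correlation are not in the documents, so both are assumed here over a range. Other inputs are 92 completers, one value per subject, and two-sided alpha 0.05. By Fisher's z, power ≈ Φ[(z_r − z_c)·√(n − 3)] plus a negligible second tail. Here z_r = atanh(r) + r/(2(n − 1)), z_c = atanh(r_c), and r_c = √(t²/(t² + n − 2)), with t the two-sided 5% critical value on n − 2 degrees of freedom.

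| Assumed share with complex plaque | n | Power, r = 0.3 | Power, r = 0.5 |
|---|---|---|---|
| 10% | 9 | 13% | 29% |
| 20% | 18 | 23% | 59% |
| 30% | 28 | 35% | 80% |
| 50% | 46 | 54% | 95% |
| 100% | 92 | 84% | >99% |

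A feature analysis is possible, but it could be weak if complex plaque is uncommon. The last row is a benchmark. Recording absence brings subjects back into the analysis of presence, but does not by itself restore 84%.

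**The case against.** The strongest reply is that the wall-area model is deliberate and tests something the plan states. H 3 speaks of plaque characteristics, A # 3 glosses these as inflammation and morphology, and morphology is given as wall area. The expected results predict exactly that relation. This stands: the model addresses the size part of H 3 and should stay. It does not reach RQ 3, which names vulnerable features.

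Several stronger readings are tempting, and the documents do not support them:

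- **That RQ 3 cannot be answered.** The same scans are planned at all three visits, so the features can be read. The analysis is unspecified, not impossible.
- **That feature values will be missing at particular visits.** The condition is worded by subject, not by visit. What can be shown is that no recording rule exists.
- **That hemorrhage is never quantified.** The Précis says it will be measured, and both tables under A # 1 give criteria for identifying it. It is absent only from the list of measurements under A # 1 and from the models.
- **That RQ 1b and H 4 lose their endpoints.** RQ 1b asks about predominance, which needs features to be identified, as A # 1 plans. H 4 states its own yardstick, the parameters of A2 and A3.

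**Conclusion.** The point holds as a mismatch between a stated research question and its analysis. Followed as written, the plan would answer RQ 3 with a slope for wall size. None of the three features named in A 1 is an outcome or predictor in a readable model, the measurement of lipid core and cap is conditional on an undefined term, and no rule covers absence.

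This conclusion rests on the text and on no sample-size figure. It assumes only that the illegible words in the association sentences do not introduce a feature variable, which the surrounding sentences make unlikely. The loss of power cannot be fixed at one number, because the documents give neither the prevalence of complex plaque nor an effect size for any feature. The range in the table is illustrative. The plan should be corrected before the images are read.

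**What to change.** **Measurement (text under A # 1).** Define complex plaque or drop the condition. On the same five slices used for wall area, read lipid core and hemorrhage (presence and area, with absence recorded as none) in every subject at 0, 18 and 36 months. Read cap thickness wherever a lipid core exists.

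**Analysis (A # 3, statistical analysis).** Add a mixed model for RQ 3 with lipid core, as area or percentage of wall area, as the dependent variable and the kinetic parameters as predictors. Make hemorrhage presence a second outcome. Use a method that allows zeros, such as a two-part model, or a logistic mixed model for presence. The plan's fallback of a log transformation cannot be applied as it stands, because log 0 is undefined. Since the kinetic parameters come from enhancing regions within the plaque, say also whether subjects without plaque enter this model. Keep the wall-area model for the size part of H 3.

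**Cost.** Extra reading time on images already planned, and a revised analysis section. No new scan or patient is needed. Precision will be limited if few subjects have these features, and the plan should say so.

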#### Assessment of Arterial Plaques by Measuring Contrast Agent Dynamics Using MR Images:

The dynamics of the contrast enhancement will be quantified using a generalized kinetic model that was proposed by Tofts, et al (45) which is based on two compartments, the blood plasma and the extravascular extracellular space (EES).  $K_{trans}$  and

model, which assumes that the signal intensity of the contrast agent in the tissue compartment and the blood plasma compartment are linearly proportional to the total concentrations of the contrast agent in the tissue,  $C_t$  and the blood plasma,  $C_p$  (42, 43, 45). This approach assumes that there is an exponential decay in the concentration of the contrast agent in the plasma described by the equation, where  $A_i$  is the initial plasma concentration and  $m_1$  is the plasma signal decay rate.

For e.g. in case of carotid arteries, the values for  $A_i$  and  $m_1$  will be determined by an ROI placed in the lumen of the jugular vein on each image in the time-course at each section location.  $C_t$  will be found by identifying regions of enhancement within the plaque. A sample of pixels large enough to cover the enhancing regions will be taken. The average of the sample pixels for each image at a given location will be used as input values for the kinetic model. The kinetic analysis will be performed using a workstation tool by the two co-investigators and repeated to assess for the inter-observer and intra-observer variability.

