#### Treatment and Clinical Follow-Up:

Patients enrolled in the “Accelerated Atherosclerosis in High Risk Population Groups: An Assessment by Magnetic Resonance Imaging” study will be evaluated in the cardiology clinic by [name],

FACC, FSCAI who is the Director of Peripheral Vascular Intervention at Emory University and treats patients with carotid artery disease. All these patients will be randomized based on the last digit of their medical record number. If the last digit will be an even number they will then be given a statin, which they will take and will also be instructed about regular exercise. Patients will be made aware of the side effects of statins and about the procedures to report these side effects. Patients with the last digit being an odd number will ONLY be advised about exercise. All patients will have regular visits and patients on a statin will be followed up and evaluated for any adverse effects of the medication and for compliance at 18 and 36 months by the study preventive cardiologist. The preventive cardiologist or any other physician involved with care of the patient may elect for more frequent follow up as well as modification or discontinuation of the study prescribed therapy if deemed necessary based on his or her best clinical judgment.

These patients will get routine clinical follow-up in the oncology (The Winship Cancer Institute Clinics) and cardiology clinics (Emory Hospital) as part of the ongoing routine clinical care.

Within five weeks of initial MRI evaluation, our recruited research that demonstrate increased blood markers and/or atherosclerosis on MRI would be subjected to life style modification ± medical (statin) therapy. Department of Cardiology would prescribe and monitor statin therapy: Rosuva (20 mg once a day) with target LDL goal < 70; non-HDL goal < 100 and Aspirin (81 mg once a day). The rational for using rosuva 20 mg is because this dosage has already been successfully used in JUPITER Trial (35). The follow-up by Cardiology department would comprise educating the patients on life style modification and also how to monitor and report any adverse drug affects which if expected would be further assessed with laboratory testing with LFT's and CBC. Any patients who suffer clinical side effects of treatment as part of our research would be taken off our study. Patients will continue to follow-up in the survivorship clinic and with the preventative cardiologist as indicated.

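### Aims 3 and 4 rest on reader-dependent MRI measures, and nothing in the plan masks the reader to arm, visit or patient identity

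*Combined protocol and SAP*

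**What the plan says.** **Kinetic measures.** The section on contrast agent dynamics assigns the work and its only quality check in one sentence: "The kinetic analysis will be performed using a workstation tool by the two co-investigators", with the readings repeated to gauge variability between and within observers. The plasma input is "determined by an ROI placed in the lumen of the jugular vein on each image". For the tissue input, enhancing regions in the plaque are identified first, and then "A sample of pixels large enough to cover the enhancing regions will be taken".

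**Vessel wall area.** Under Specific Aims, A # 1: "The vessel wall area and total artery area will be determined by tracing contours along the boundaries". It adds: "The areas will be calculated using a semi-automated analysis tool". Five contiguous images are analysed and averaged. No one is named as the tracer.

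**Visits.** The section on baseline, intermediate and final MRI says "Anatomical landmarks will be used to match images (baseline, intermediate and final) in the same patient". It does not say whether the reader knows which scan is which.

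**Arm.** Under Treatment and Clinical Follow-Up, an even final digit of the record number leads to a statin, and "Patients with the last digit being an odd number will ONLY be advised about exercise". The Examination Plan Overview and A # 4 of the Specific Aims also describe lifestyle modification without a statin as the comparator. The Aims section, at A 4, instead names a placebo.

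**Expected result.** The expected results for A # 3 anticipate favourable change under treatment. Those for A # 4 anticipate that the statin regimen will do better.

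**The concern.** Aim 3 is about change from baseline in these readings, and Aim 4 is about the difference between arms. Both are exposed if the person drawing a contour or choosing pixels knows the visit or the arm and holds the expectation that the protocol states. Knowledge of visit can tilt the change over time, and knowledge of arm can tilt the comparison.

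The one planned check does not address this. Repeat readings show how closely readers agree with each other and with themselves. Two readers who lean the same way can agree well and both be wrong. Using each patient as his or her own control, as A # 4 describes, gives no protection if the reader knows which scan came first.

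The serum markers are measured in a laboratory and are less exposed.

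**Working it through.** **1. The plan's own figure.** The plan gives no figure for reader error. The figure that sets the trial's size is in Sample Size: 92 subjects, three time points, effect size 0.28, alpha 0.05, power above 99%. As a one-way ANOVA with 92 per time point:

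- noncentrality = 3 × 92 × 0.28² = 21.6, with 2 and 3 × 91 = 273 degrees of freedom
- power = 99.0%, and 92 is the smallest number that reaches 99%

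The figure reproduces, and masked reading would not alter it.

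**2. Search for masking.** No section provides masked reading, removal of identifiers, random reading order or an independent reader. The only mention of double-blinding is in the title of a cited study in the reference list.

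**3. Sensitivity of wall area to the contour.** Inputs from High Resolution Anatomical Images: field of view 120 to 160 mm right-left, matrix 512. Assumed, because the documents give no vessel dimensions: lumen radius Ri = 3 mm, outer radius Ro = 4 to 5 mm.

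- Pixel = 120/512 to 160/512 = 0.23 to 0.31 mm; half a pixel = 0.117 to 0.156 mm
- Wall area = π(Ro² − Ri²)

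| Ro (mm) | Wall area (mm²) | Change, 0.117 mm shift | Change, 0.156 mm shift |
|---|---|---|---|
| 4.0 | 22.0 | −13.2% | −17.5% |
| 4.5 | 35.3 | −9.3% | −12.3% |
| 5.0 | 50.3 | −7.2% | −9.6% |

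This moves the outer contour inward around its full circumference, with the lumen contour fixed. To survive the five-slice average, the shift would have to recur across the slices.

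**4. When a shift becomes bias.** Observed change = true change + (reader shift at follow-up − reader shift at baseline). A constant drawing habit largely cancels in this difference. It also cancels between arms if it is the same in both. Only a shift that differs by visit affects Aim 3, and only one that differs by arm affects Aim 4.

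**5. Kinetic readings.** DCE 2D SPGRI gives a 256 × 160 matrix. Taking 256 as the right-left direction, pixels are 120/256 to 160/256 = 0.47 to 0.63 mm. In the other direction the field is 0.75 × 120 = 90 to 0.75 × 160 = 120 mm, so 90/160 to 120/160 = 0.56 to 0.75 mm. On the assumed radii the wall is 4 − 3 = 1 to 5 − 3 = 2 mm thick, or about 1 to 4 pixels (1/0.75 to 2/0.47). Pixel choice therefore has room to matter, but the documents do not allow a size to be put on Ktrans.

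**6. What a differential shift would do to the test.** The documents give no SD, no expected wall-area change and no between-arm effect size, so the shift b (in SDs) is an assumption. The calculation uses a noncentral t test, two-sided 0.05, with no true effect. Noncentrality is b√(46/2) for the arm difference, assuming 92 split as 46 per arm, and b√92 for within-patient change, with b in SDs of the change score.

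| b | Arm difference, p < 0.05 | Change over time, p < 0.05 |
|---|---|---|
| 0 | 5.0% | 5.0% |
| 0.1 | 7.6% | 15.8% |
| 0.2 | 15.8% | 47.5% |
| 0.3 | 29.6% | 81.2% |

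These t tests are simpler than the planned mixed models. The table shows consequences if a shift occurs; it is not an estimate that one will.

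**The case against.** The strongest reply is that the plan is silent on masking and nowhere says that readers know visit or arm. The contour tool is semi-automated and five slices are averaged, which leaves less room for free-hand drift. Not every reading can be masked, because the baseline MRI helps decide who starts treatment, within five weeks.

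Much of this stands, and it rules out several stronger readings that a reader might infer:

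- **That the co-investigators trace the contours.** They are named only for the kinetic analysis.
- **That the images carry the record number or a visit label.** No section says which identifiers the images carry. The documents show only that whoever sees the number can work out the arm.
- **That the trial is plainly open-label.** Three sections describe a comparator without a statin and no placebo supply is described, but A 4 in the Aims names a placebo. The sections must be reconciled. Even a placebo would not hide visit order, and the digit rule would still disclose the arm.
- **That a half-pixel preference produces a treatment effect.** The 7% to 18% measures sensitivity on assumed radii. The documents offer nothing to compare it with, and a constant shift largely cancels.
- **That the results will be biased.** The documents support a risk of bias, not its presence.

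The core is not answered. A semi-automated tool and averaging limit random error but do not mask the reader, and the need for an early baseline read does not prevent a later masked outcome reading.

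**Conclusion.** The concern holds in this form: the MRI measures behind Aims 3 and 4 depend on reader judgement, the plan states the direction it expects, and nothing written keeps arm, visit or identity from the reader. Differential reader bias is therefore possible in both change over time and the arm difference, and the planned repeat readings would not detect a bias that the readers share.

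Its size is unknown. The wall-area percentages rest on assumed radii, and the false-positive rates on assumed shifts and, for the arm comparison, an even split of 92. The change should be made before outcome readings begin, because masking cannot be restored once unmasked readings enter the analysis.

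**What to change.** Separate two kinds of reading. The baseline read needed to start treatment goes ahead as now and is not used as outcome data. For every outcome reading (wall, plaque component and kinetic):

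1. Export each patient's available scans under study codes, with record number, name, scan date and visit label removed. Include patients who leave early, whose sets will never be complete.
2. Match slices by landmarks within the coded set.
3. Read in random order with the same planned readers, re-reading baselines in coded form. Name the contour reader, who is not identified at present.
4. Lock all measurements before codes are linked to visit and arm.

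State this in the sections on baseline, intermediate and final MRI, on plaque measurement under A # 1, and on contrast agent dynamics. Reconcile the description of the comparator in the Aims with the later sections.

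The cost is a de-identified export and a random code list. Scans, readers and sample size do not change. Outcome readings wait for follow-up scans, baselines are read twice, and a reader who did the initial baseline read may recognise it.
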